Bone scan (Optional)	Only in adult Cohort B pts Section 6.2.3	X								
Renal stone events	Section 6.3.2									Continuous
Review/record AEs	Section 6.5.6.2									Continuous
Prior and concomitant medications	Section 5.3									Continuous

Abbreviations: ADA=antidrug antibody; AE=adverse event; AGXT=alanine-glyoxylate aminotransferase gene; D=day; DNA=deoxyribonucleic acid; ECG=electrocardiogram; hrs=hours; LFTs=liver function tests; M=Month; Opt=optional; PD=pharmacodynamic; PE=physical examination; PH1=primary hyperoxaluria type 1; PK=pharmacokinetic; POx=plasma oxalate; pts=patients; SAE=serious adverse event; wk=week; y=year(s)

* During periods of time when the COVID-19 pandemic impedes the ability of patients to travel to the study site, the visit window is expanded to ±14 days after Week 2.

Notes:

- One month is defined as 28 days.
- Only SAEs are collected in the Screening period. Starting on D1, all AEs (including SAEs) are collected.
- Assessments are to be performed prior to dosing, where applicable. When scheduled at the same time points and where feasible, the assessments of vital signs and 12-lead ECGs should be performed before physical examinations and blood sample collections.
- Visits and study drug dosing may be conducted offsite where applicable country and local regulations and infrastructure allow (at the discretion of the Investigator, based on safety and tolerability), provided the patient has tolerated a dose of lumasiran administered in the clinic. If a visit is conducted offsite, a body system assessment may be performed in lieu of a physical examination.
- In situations where a study visit is unable to be completed (either at the site or offsite by a healthcare professional), the Investigator (or delegate) will verbally contact the patient within the study visit window to assess concomitant medications, renal stone events, adverse events, and healthcare utilization.
- Patients who discontinue from study drug prior to completion of the Month 6 assessments should be encouraged to remain on the study and complete assessments (including 24-hour urine collections but excluding PK assessments) through Month 6. They will also be asked to complete safety follow-up visits once every 3 months, per the safety follow-up schedule (see Table 3 or Table 4), for up to 12 months after the last dose of lumasiran (Section 3.3.1). See Section 4.3.1 for instructions for patients who discontinue study drug.

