- Visits and study drug dosing may be conducted offsite where applicable country and local regulations and infrastructure allow (at the discretion of the Investigator, based on safety and tolerability), provided the patient has tolerated a dose of lumasiran administered in the clinic. If a visit is conducted offsite, a body system assessment may be performed in lieu of a physical examination.
- In situations where a study visit is unable to be completed (either at the site or offsite by a healthcare professional), the Investigator (or delegate) will verbally contact the patient within the study visit window to assess concomitant medications, renal stone events, adverse events, and healthcare utilization.
- Patients who discontinue study drug after Month 6 will be asked to return for their next scheduled visit to complete ET assessments and to complete safety follow-up visits once every 3 months, per the safety follow-up schedule (see Table 3 or Table 4), for up to 12 months after the last dose of lumasiran (Section 3.3.1). See Section 4.3.1 for instructions for patients who discontinue study drug.
- Urine collections are only performed in patients who are able to produce urine, ie, ability to produce ≥ 100 ml per day.

Table 3: Schedule of Assessments – Long-term Extension Period (Month 36 to End of Study): Patient Weight <10 kg
Patients whose weight increases to ≥10 kg continue monthly dosing until the next visit that coincides with Table 4. Patients will then follow Table 4 until the end of the study.

Study Period		Long-term Extension Period															EOT	EOS/ET	Safety Follow-up						
Study Visit		M36	M37; M38	M39	M40; M41	M42	M43; M44	M45	M46; M47	M48	M49; M50	M51	M52; M53	M54	M55; M56	M57	M60	(Pts who DC treatment)							
Study Day (±Visit Window)	Notes	1009 (±14)	1037, (±14)	1065 (±14)	1093 (±14)	1121, (±14)	1149 (±14)	1177 (±14)	1205, (±14)	1233 (±14)	1261 (±14)	1289, (±14)	1317 (±14)	1345 (±14)	1373, (±14)	1401 (±14)	1429 (±14)	1457, (±14)	1485 (±14)	1513 (±14)	1541, (±14)	1569 (±14)	1597 (±14)	1681 (±14)	Every 84 days (±14)
Full PE	Section 6.5.3	X				X						X				X			X						
Abbreviated PE	Section 6.5.3				X					X					X			X		X					
Height/length	Section 6.5.2	X		X		X			X			X		X		X			X	X	X				
Body weight	Section 6.5.2	X	X	X	X	X	X	X	X	X	X	X	X	X	X	X	X	X	X	X					
Vital signs	Section 6.5.1	X	X	X	X	X	X	X	X	X	X	X	X	X	X	X	X	X	X	X					
12-lead ECG	Triuplicate. Section 6.5.4	X										X							X						

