3.3.1. Definition of End of Study for an Individual Patient

A patient is considered to have reached the end of the study if:

- the patient has completed the end of study (EOS; Month 60) visit, or
- the patient has completed 12 months of monitoring following the final lumasiran dose

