4.3.1. Discontinuation of Study Drug or Declining Procedural Assessments

Reasons for discontinuation of study drug may include any of the following:

- Significant violation of the protocol

- AE
- Non-adherence to treatment regimen
- Pregnancy
- Lost to follow-up
- Other reason (non-AE)
- Or, study is terminated by the Sponsor

If possible, the Investigator will confer with the Sponsor or Medical Monitor before discontinuing dosing in the patient. Patients who are pregnant will be discontinued from study drug dosing immediately (see Section 6.5.6.7 for reporting and follow-up of pregnancy). A positive urine pregnancy test should be confirmed by a serum pregnancy test prior to discontinuing the study drug.

If a patient discontinues dosing due to an AE, including SAEs, the event should be followed as described in Section 6.5.6. When a patient discontinues study drug dosing, the primary reason must be recorded in the electronic case report form (eCRF). Patients who discontinue study drug and remain on study may receive treatment consistent with local standard practice for their disease per Investigator judgement, as applicable.

Patients who discontinue from study drug during the 6-month primary analysis period (defined as the time the first dose of study drug is administered on Study Day 1 through completion of the Month 6 assessments) will be encouraged to remain on the study and complete assessments (including 24-hour urine collections, but excluding PK assessments) through Month 6 (see Table 1). They will also be asked to complete safety follow-up visits, once every 3 months, per the safety follow-up schedule (see Table 3 or Table 4) for up to 12 months after the last dose of lumasiran.

Patients who discontinue study drug after Month 6 will be asked to return for their next scheduled visit to complete early termination (ET) assessments and complete safety follow-up visits, once every 3 months, per the safety follow-up schedule (see Table 3 or Table 4) for up to 12 months after the last dose of lumasiran.

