6.5.6.2. Eliciting and Recording Adverse Events

Eliciting Adverse Events

The patient or legal guardian should be asked about medically relevant changes in the patient’s health since the last visit. The patient or legal guardian should also be asked if the patient has been hospitalized, had any accidents, used any new medications, or changed concomitant medication routines (both prescription and over-the-counter). In addition to patient observations, AEs will be documented from any clinically relevant laboratory findings, physical examination findings, ECG changes, or other findings that are relevant to patient safety.

Recording Adverse Events

The Investigator is responsible for recording non-serious AEs that are observed or reported by the patient after administration of the first dose of study drug regardless of their relationship to study drug through the end of study. Non-serious AEs will be followed until the end of study. Events occurring after signing of the ICF and before study drug administration will be captured as medical history (see Section 6.1), while AEs that occur after study drug administration, and baseline events that worsen after study drug administration, must be recorded as AEs.

The Investigator is responsible for recording SAEs that are observed or reported by the patient after the time when the informed consent is signed regardless of their relationship to study drug through the end of study. SAEs will be followed until satisfactory resolution, until baseline level is reached, or until the SAE is considered by the Investigator to be chronic or the patient is stable, as appropriate.

All AEs must be recorded in the source records for the clinical study center and in the eCRF for the patient, whether or not they are considered to be drug-related. Each AE must be described in detail: onset time and date, description of event, severity, relationship to study drug, action taken, and outcome (including time and date of resolution, if applicable).

For SAEs, record the event(s) on both the eCRF and the SAE form.

For AEs that are considered AEs of clinical interest (see Section 6.5.6.1), the supplemental AEs of Clinical Interest eCRF should be completed. Additional clinical and laboratory information may be collected. Refer to CRF completion guidelines for details on reporting events in the supplemental AEs of Clinical Interest eCRF.

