7.6.1. Adverse Events

The primary safety parameter is treatment emergent AEs. A treatment emergent AE will be defined as an AE that occurs or worsens on/after the first dose date/time of lumasiran through 84 days after the last dose. In addition, any AE that worsened in intensity or was subsequently considered related to lumasiran will be considered treatment emergent.

AEs will be classified using the Medical Dictionary for Regulatory Activities (MedDRA Version 21.1 or later) and displayed in tables using System Organ Class (SOC) and Preferred Terms (PT). All treatment emergent AEs hereafter will be referred to as AEs in this document.

An overview table of AEs will be generated. The overview table will include the number and percentage of patients in categories such as, but not limited to:

- At least 1 AE
 - At least 1 drug related AE
- At least 1 severe AE

- At least 1 drug related severe AE
- At least 1 Serious Adverse Event (SAE)
 - At least 1 drug related SAE
- At least 1 AE leading to treatment discontinuation
 - At least 1 drug related AE leading to treatment discontinuation
- At least 1 AE leading to study withdrawal
 - At least 1 drug related AE leading to study withdrawal
- At least 1 AE leading to treatment interruption
 - At least 1 drug related AE leading to treatment interruption
- Death

Tabulations by System Organ Class (SOC) and Preferred Term (PT) displaying the number of patients (percentage) and total events will be produced for the following tables:

- All AEs
- Severe AEs
- AEs by Maximum Severity
- AEs related to treatment
- AEs related to treatment by Maximum Severity
- All SAEs
- SAEs related to treatment
- AEs leading to treatment discontinuation
- AEs leading to treatment interruption
- AEs leading to study withdrawal

Tabulations by PT in decreasing order of frequency will be generated for the following tables:

- All AEs
- All SAEs
- AEs related to treatment
- SAEs related to treatment

There will also be an All AE table generated displaying rates of AEs adjusted for exposure-time.

Patients who report multiple occurrences of the same AE (preferred term) will be classified according to the most severe occurrence or most related.

Separate listings will be provided for deaths, SAEs, and AEs leading to discontinuation of study drug, withdrawal of study drug and/or dose interruption. By-patient AE listings will be provided.

Additional summaries will also be generated:

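### The SAP's AE and SAE tables stop 84 days after the last dose, but safety follow-up can run 12 months, so a new late SAE judged unrelated is listed but not tabulated

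*SAP*

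**What the plan says.** **The analysis window.** SAP 7.6.1 (Adverse Events) defines a treatment-emergent AE as one that occurs or worsens from the first dose "through 84 days after the last dose". It gives two further routes in: "In addition, any AE that worsened in intensity or was subsequently considered related to lumasiran will be considered treatment emergent". It then states: "All treatment emergent AEs hereafter will be referred to as AEs in this document". The overview table, the SOC and preferred-term tables (including those for SAEs), and the exposure-adjusted AE table all follow that sentence.

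**The collection period.** Protocol 6.5.6.2 has non-serious AEs (from first dose) and SAEs (from consent) recorded "regardless of their relationship to study drug through the end of study". Protocol 4.3.1 asks patients who discontinue study drug to attend safety visits every three months "for up to 12 months after the last dose of lumasiran". Protocol 3.3.1 makes this one of the two ways an individual reaches the end of the study: "the patient has completed 12 months of monitoring following the final lumasiran dose".

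**Other SAP text that bears on the point.**
- SAP 5.2 says that summaries for a study period take in all data collected in that period, and that all CRF data are listed.
- SAP 4.1 runs the Long-term Extension Period through the end of the study.
- SAP 6.1 tabulates reasons for withdrawal.
- SAP 7.6.1 itself plans separate listings of deaths and SAEs.
- SAP 7.6.2 ends drug exposure at 84 days after the last dose, or at the analysis cut-off or end of study if sooner.

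**The concern.** The protocol sets up an off-drug safety follow-up of up to a year and requires every event in it to be recorded. The SAP's tables use only the first 84 days of it for new events, unless one of the two extra routes applies. No table is planned for events that start later.

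This matters more here than in a controlled trial. There is no comparator, so the safety conclusion rests on counts within one open-label arm. For a new late SAE that does not worsen, entry to the tables depends on the investigator's yes-or-no causality judgement. The patients concerned are those who stopped the drug, which is the group the 12-month follow-up was designed to watch. With 20 planned patients, one patient more or less in a count is visible.

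**Working it through.** The plan gives no figure of its own on this point, so there is nothing to reproduce first. The check sets the window against the follow-up.

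**Inputs**
- Window: 84 days after the last dose (SAP 7.6.1).
- Follow-up after stopping: up to 12 months (Protocol 4.3.1).
- Month length: "One month is defined as 28 days" (notes to the protocol's schedules of assessments), so 12 × 28 = 336 days.
- Safety follow-up visits: every 84 days, ±14 (Protocol Tables 3 and 4).
- Completers: last dose at Month 57, Day 1597; end-of-study visit at Month 60, Day 1681; both ±14 days (Protocol Tables 3 and 4).
- Planned size: 20 patients, at least 6 per cohort (SAP 5.1).

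**Patients who discontinue**

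Share outside the window = (follow-up days − 84) / follow-up days.

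| Follow-up actually completed | Days outside | Share outside |
|---|---|---|
| 84 days | 0 | 0% |
| 168 days | 84 | 50% |
| 252 days | 168 | 66.7% |
| 336 days (full) | 252 | 75% |

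The full-follow-up figure does not depend much on the 28-day month: (360 − 84)/360 = 76.7% and (365 − 84)/365 = 77.0%. Of the four nominal safety visits (84, 168, 252 and 336 days after the last dose), the last three fall outside.

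The gap can also arise inside the Primary Analysis Period. For a patient whose only dose is on Day 1, the window closes on Day 1 + 84 = Day 85. If that patient stays to the Month 6 visit on Day 169, the last 169 − 85 = 84 days are outside.

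**Completers**

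Nominal gap from last dose to last visit: 1681 − 1597 = 84 days, so nothing is cut. With both visits at the edges of their windows, the gap runs from (1681 − 14) − (1597 + 14) = 56 days to (1681 + 14) − (1597 − 14) = 112 days. At the extreme, 112 − 84 = 28 days fall outside.

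**Weight of one patient**

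1/20 = 5 percentage points overall. With at least 6 patients in each cohort, a cohort has 6 to 14, so one patient is 1/14 = 7.1 to 1/6 = 16.7 percentage points of a cohort. This is the size of one omission, not an estimate of how many will occur.

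**Following one event through the SAP**

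Take a new SAE with a complete onset date 100 days after the last dose that is judged unrelated and does not worsen.
- SAP 7.6.1, treatment-emergent definition: not met.
- SAP 7.6.1, overview and SOC/preferred-term tables: not counted.
- SAP 5.2, listings of all CRF data: listed.
- SAP 5.2, period summaries of all data collected: would be counted, if this rule governed.
- SAP 6.1, reasons for withdrawal: reached only if the event ended participation and was recorded as the reason.

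The two sections give different answers for the same event, and the SAP does not say which prevails.

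**The case against.** The best defence is that nothing is lost. All CRF data are listed, deaths and SAEs have their own listings, and in a 20-patient descriptive study each late SAE would be seen individually. That stands: the gap is in tabulation, not in reporting.

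A reader might go further and infer that late deaths and unrelated SAEs appear in no planned summary. The documents do not support that. The overview row is labelled simply as death and has no window of its own; the death and SAE listings have none either. Their place in a section that has just redefined AE makes their scope unclear, but does not show that late events are excluded. A death that ends participation could also appear among the withdrawal reasons in SAP 6.1, and SAP 5.2 taken alone would bring late events into the period summaries.

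A reader might also infer that causality is the only gate. It is not: worsening in intensity is a second route with no stated time limit, and SAP 5.5 treats AEs with missing or partial dates as treatment emergent unless they clearly preceded the first dose. Causality decides only for a new, fully dated late event that does not worsen.

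Two further defences hold. The 84-day limit equals the three-month maintenance dosing interval and matches the exposure definition in SAP 7.6.2, so numerator and denominator of the exposure-adjusted rates agree. The liver-test categories and eDISH plots in SAP 7.6.3 use any post-baseline value, so not all off-drug safety data are left to listings.

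What remains unanswered is the new late SAE judged unrelated. It has no assured place in any table, and a non-fatal one that does not end participation lacks even the withdrawal-reason route.

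**Conclusion.** The point holds in a limited form. Under SAP 7.6.1, a new SAE that starts more than 84 days after the last dose, does not worsen and is judged unrelated is listed but not tabulated. Up to 75% of a fully completed post-discontinuation follow-up lies in that zone. The figure is a ceiling: it assumes 28-day months and all 12 months completed, and the protocol promises only up to 12. For completers the gap is nominally zero and at most 28 days within the ±14-day visit windows.

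Whether deaths are affected cannot be settled from the text, because the scope of the Death row and of the death and SAE listings is not stated and SAP 5.2 conflicts with SAP 7.6.1. That is a reason to clarify, not evidence that deaths are left out. The 84-day definition itself is sound. The documents do not allow an estimate of how many events would be missed; the number depends on how many patients discontinue and how long they are followed. This is an inexpensive improvement to the SAP and does not put the main AE tables in doubt.

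**What to change.** In SAP 7.6.1:
1. Keep the 84-day treatment-emergent definition for the main AE tables and the exposure-adjusted rates.
2. State that the Death row and the death and SAE listings cover all events from first dose to end of study, and that for the other AE tables SAP 7.6.1 takes precedence over the general rule in SAP 5.2.
3. Add one table, by cohort, of deaths and SAEs with onset more than 84 days after the last dose, showing how many patients were followed beyond that point.

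The cost is a few sentences and one extra table from data already collected. Reported counts of deaths or SAEs may be slightly higher.

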7.6.2. Dosing and Extent of Exposure

Summaries of exposure will include the following characteristics such as, but not limited to: the total number of doses received per patient, mean number of doses per subject, cumulative number of doses received, duration of drug exposure (months), cumulative drug exposure time (months), the total dose administered (mg) and total volume administered (mL).

Definition of drug exposure (days) will be defined as the minimum of [Exposure time= (date of last exposure – date of first dose +1)] where date of last exposure will represent either the date of the last dose administered dose +84, analysis cut-off date or end of study date, whichever occurs first. The exposure during the Primary Analysis Period will be right censored; that is, the date of the last exposure will not be later than the first date of dosing in the Extension Period.

Dose interruptions and compliance are not taken into account.

7.6.3. Clinical Laboratory Data

Clinical laboratory parameters will be expressed in Standard International (SI) units. Laboratory data collected and recorded as below the lower limit of detection (LLOD) will be set to the LLOD for calculation of summary statistics. Summaries will only include data from central laboratory. For any local collections of LFTs, these will be included in a separate data listing. Key laboratory parameters will be graded according to NCI CTCAE v5.0 or later.

Summaries for each lab parameter (hematology, chemistry, liver function tests, and urinalysis) that are continuous variables, will have a tabular summary of descriptive statistics at each scheduled visit. Descriptive statistics include actual value, change from baseline and percent change from baseline at each scheduled visit.

Shift tables will be generated to summarize shifts from baseline category to the worst post-baseline category with directionality specified (eg hyper and hypo), including eGFR when applicable.

Clinical laboratory tests with normal ranges will be classified as Low, Normal, and High. For these tests, abnormal values will be flagged in the listings with H when the value is higher than

the upper limit of the reference ranges and with L when the value is lower than the lower limit of the reference ranges.

For hematology and chemistry labs, summary tables of potentially clinically significant abnormalities may also be provided.

All laboratory data will be presented in data listings. Separate listings will be included for those laboratory data collected from local labs such as LFTs. Out of range laboratory results will be identified in listings.

LFTs: A listing will be generated for all patients with abnormal liver function tests as defined by alanine aminotransferase (ALT)>3xULN, aspartate aminotransferase (AST)>3xULN or total bilirubin >2x ULN at any visit, where age specific ULN (when applicable) may be used.

A tabular summary for LFTs will be generated to summarize the number and associated percentage of patients in each of the categories at any post-baseline visit:

- Within normal limit (WNL), $1 < \text{ALT} \leq 3$, $3 < \text{ALT} \leq 5$, $5 < \text{ALT} \leq 10$, $10 < \text{ALT} \leq 20$, $\text{ALT} > 20 \times \text{ULN}$
- WNL, $1 < \text{AST} \leq 3$, $3 < \text{AST} \leq 5$, $5 < \text{AST} \leq 10$, $10 < \text{AST} \leq 20$, $\text{AST} > 20 \times \text{ULN}$
- WNL, $1 < \text{ALT or AST} \leq 3$, $3 < \text{ALT or AST} \leq 5$, $5 < \text{ALT or AST} \leq 10$, $10 < \text{ALT or AST} \leq 20$, $\text{AST or ALT} > 20 \times \text{ULN}$
- WNL, $\text{ALP} > 1.5 \times \text{ULN}$
- WNL, $1.5 < \text{Total Bilirubin} \leq 2$, $2 < \text{Total Bilirubin} \leq 3$, $3 < \text{Total Bilirubin} \leq 5$ and $\text{Total Bilirubin} > 5 \times \text{ULN}$

eDISH plots of peak bilirubin at any time versus peak ALT or AST at any time will also be presented.

For selected labs (eg ALT/ULN and AST/ULN), a table and figure of the values across the entire study will be generated.

